7.2.2 Reporting of Pregnancy and Lactation to the Sponsor

Although pregnancy and lactation are not considered adverse events, it is the responsibility of investigators or their designees to report any pregnancy or lactation in a subject (spontaneously reported to them) that occurs during the trial.

Pregnancies and lactations that occur after the consent form is signed but before treatment allocation/randomization must be reported by the investigator if they cause the subject to be excluded from the trial, or are the result of a protocol-specified intervention, including but not limited to washout or discontinuation of usual therapy, diet, placebo treatment or a procedure. Pregnancies and lactations that occur from the time of treatment allocation/randomization through 14 days following cessation of Sponsor's product must be reported by the investigator. All reported pregnancies must be followed to the completion/termination of the pregnancy. Pregnancy outcomes of spontaneous abortion, missed abortion, benign hydatidiform mole, blighted ovum, fetal death, intrauterine death, miscarriage and stillbirth must be reported as serious events (Important Medical Events). If the pregnancy continues to term, the outcome (health of infant) must also be reported.

Such events must be reported within 24 hours to the Sponsor either by electronic media or paper. Electronic reporting procedures can be found in the EDC data entry guidelines. Paper reporting procedures can be found in the Investigator Trial File Binder (or equivalent).

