^c If the subject is receiving anticoagulant therapy, the PT or partial thromboplastin time (PTT) should be within the therapeutic range of intended use of anticoagulants.

8. Have voluntarily agreed to participate by giving written informed consent. The subject may also provide consent for Future Biomedical Research. However, the subject may participate in the main trial without participating in Future Biomedical Research
9. Female subjects of childbearing potential must have a negative urine or serum pregnancy test at Screening and again within 72 hours prior to receiving the first dose of study treatment. If the urine test is positive or cannot be confirmed as negative, a serum pregnancy test will be required. The serum pregnancy test must be negative for the subject to be eligible.
10. Female subjects of childbearing potential (refer to Section 5.7.2) must be willing to use an adequate method of contraception as outlined in Section 5.7.2– Contraception, for the course of the study through 120 days after the last dose of study medication.
 Note: Abstinence is acceptable if this is the usual lifestyle and preferred contraception for the subject.
11. Male subjects of childbearing potential (refer to Section 5.7.2) must agree to use an adequate method of contraception as outlined in Section 5.7.2– Contraception, starting with the first dose of study therapy through 120 days after the last dose of study therapy.

Note: Abstinence is acceptable if this is the usual lifestyle and preferred contraception for the subject.

12. Submit archived or fresh tumor sample during screening period as specified in the Procedures Manual.

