5.8.2 Contraception

MK-1966 and SD-101 may have adverse effects on a fetus in utero. Furthermore, it is not known if either drug has transient adverse effects on the composition of sperm. Non-pregnant, non-breast-feeding women may be enrolled if they are considered highly unlikely to conceive.

Female subjects will be considered of non-reproductive potential if they are either:

- (1) postmenopausal (defined as at least 12 months with no menses without an alternative medical cause; in women < 45 years of age a high follicle stimulating hormone (FSH)

level in the postmenopausal range may be used to confirm a post-menopausal state in women not using hormonal contraception or hormonal replacement therapy. In the absence of 12 months of amenorrhea, a single FSH measurement is insufficient.);

OR

(2) have had a hysterectomy and/or bilateral oophorectomy, bilateral salpingectomy or bilateral tubal ligation/occlusion, at least 6 weeks prior to screening;

OR

(3) has a congenital or acquired condition that prevents childbearing.

Female and male subjects of reproductive potential must agree to avoid becoming pregnant or impregnating a partner, respectively, while receiving study drug and for 120 days after the last dose of study drug by complying with one of the following:

(1) practice abstinence[†] from heterosexual activity;

OR

(2) use (or have their partner use) acceptable contraception during heterosexual activity.

Acceptable methods of contraception are[‡]:

Single method (one of the following is acceptable):

- intrauterine device (IUD)
- vasectomy of a female subject's male partner
- contraceptive rod implanted into the skin

Combination method (requires use of two of the following):

- diaphragm with spermicide (cannot be used in conjunction with cervical cap/spermicide)
- cervical cap with spermicide (nulliparous women only)
- contraceptive sponge (nulliparous women only)
- male condom or female condom (cannot be used together)
- hormonal contraceptive: oral contraceptive pill (estrogen/progestin pill or progestin-only pill), contraceptive skin patch, vaginal contraceptive ring, or subcutaneous contraceptive injection

For this trial, male subjects will be considered to be of non-reproductive potential if they have azoospermia (whether due to having had a vasectomy or due to an underlying medical condition).

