[†]Abstinence (relative to heterosexual activity) can be used as the sole method of contraception if it is consistently employed as the subject's preferred and usual lifestyle and if considered acceptable by local regulatory agencies and ERCs/IRBs. Periodic abstinence (e.g., calendar, ovulation, sympto-thermal, post-ovulation methods, etc.) and withdrawal are not acceptable methods of contraception.

‡If a contraceptive method listed above is restricted by local regulations/guidelines, then it does not qualify as an acceptable method of contraception for subjects participating at sites in this country/region.

Subjects should be informed that taking the study medications may involve unknown risks to the fetus (unborn baby) if pregnancy were to occur during the study. In order to participate in the study subjects of childbearing potential must adhere to the contraception requirement (described above) from the day of study medication initiation (or 14 days prior to the initiation of study medication for oral contraception) throughout the study period up to 120 days after the last dose of trial therapy. If there is any question that a subject of childbearing potential will not reliably comply with the requirements for contraception, that subject should not be entered into the study.

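### The explicit pregnancy-reporting window closes 14 days after treatment, contraception runs for 120 days, and the protocol's other reporting sentences do not clearly cover the difference

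*Combined protocol and SAP*

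**What the plan says.** **Reporting.** Section 7.2.2 contains two duties. It opens by making investigators responsible "to report any pregnancy or lactation in a subject (spontaneously reported to them) that occurs during the trial", with no day limit. Its next paragraph says that pregnancies from treatment allocation "through 14 days following cessation of Sponsor's product must be reported by the investigator". Reports are due within 24 hours, and every reported pregnancy is followed to its end.

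**Contraception.** Section 5.1.2 requires it of women "for the course of the study through 120 days after the last dose of study medication" and of men "starting with the first dose of study therapy through 120 days after the last dose of study therapy". Section 5.8.2 has both sexes avoid pregnancy "while receiving study drug and for 120 days after the last dose of study drug", and repeats the requirement as "throughout the study period up to 120 days after the last dose of trial therapy". Its reason is that "MK-1966 and SD-101 may have adverse effects on a fetus in utero"; effects on sperm are described as unknown.

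**Related text.**
- Section 5.8.3 deals with a female subject only if she conceives on treatment. For a male subject's partner it asks for the pregnancy to be reported and followed, sets no day limit of its own, and refers to 7.2.2.
- Section 7.2.3.1 makes a serious adverse event judged related to the product reportable at any time, and lists congenital anomaly as a seriousness criterion.
- No section sets a 120-day pregnancy-reporting window.

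**The concern.** The protocol asks subjects to avoid conception for 120 days because of a possible fetal effect, yet the one sentence that puts an end date on mandatory pregnancy reporting stops at 14 days. A site that takes that sentence as the operative rule could leave unreported a pregnancy that a female subject conceives between day 15 and day 120. Because 7.2.2 requires follow-up to completion only for reported pregnancies, the outcome could be missed as well. This is a first-in-human antibody trial, and Section 4.2.2.2.1 records that specific staining in the tissue cross-reactivity study was limited to the placenta. Exposed pregnancies will be few, so each one is informative. The issue is safety data collection. Sample size, DLT assessment and the planned analyses are unaffected.

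**Working it through.** The plan gives no figure of its own for the gap, so there is none to reproduce.

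**Inputs**
- Explicit reporting window after cessation: 14 days (7.2.2).
- Contraception period after last dose: 120 days (5.1.2, 5.8.2).
- Last planned dose (Table 5): MK-1966 is given on Day 1 and then every 3 weeks for 7 more doses, so 1 + 7 × 21 = Day 148. SD-101 is given on Day 22 and then every 3 weeks for 6 more doses, so 22 + 6 × 21 = Day 148.

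**Step 1: post-dose gap.** 120 − 14 = 106 days, and 106/120 = 88%.

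**Step 2: gap as a share of the whole contraception period.** On-treatment pregnancies are reportable, so the denominator from first dose is (last dose day − 1) + 120.

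| Last dose | Contraception period (days) | Outside explicit window |
|---|---|---|
| Day 15 | 14 + 120 = 134 | 106/134 = 79% |
| Day 64 | 63 + 120 = 183 | 106/183 = 58% |
| Day 148 (8 cycles) | 147 + 120 = 267 | 106/267 = 40% |

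**Step 3: other windows.** A window matched to the 30-day safety follow-up would leave 120 − 30 = 90 days (90/120 = 75%). A window matched to the contraception period would leave none.

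**Step 4: does other text cover days 15 to 120?**

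| Text | Female subject | Partner of male subject |
|---|---|---|
| 7.2.2, opening sentence | Possibly, if the subject volunteers it and is still in the trial | Not mentioned |
| 7.2.2, 14-day sentence | No | Not mentioned |
| 5.8.3 | No, on treatment only | Yes on its face, but refers to 7.2.2 |
| 7.2.3.1, related events at any time | Only a serious event judged related | Only a serious event judged related, if it reaches the investigator |

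**Step 5: persistence of MK-1966 at day 14 (illustrative).** Assume one compartment, so that the fraction remaining is exp(−t × CL/Vss).
- Predicted human values in Table 1 (CL 2.4 mL/day/kg, Vss 78 mL/kg): half-life = ln 2 × 78/2.4 = 22.5 days; exp(−14 × 2.4/78) = 65% at day 14; exp(−120 × 2.4/78) = 2.5% at day 120.
- Observed human values for MK-7089 (CL 2.1, Vss 93.9): exp(−14 × 2.1/93.9) = 73% at day 14.
- Monkey half-life of 12.7 days: 0.5^(14/12.7) = 47% at day 14.

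Roughly half or more of the antibody is still present when the explicit window closes. This says nothing about SD-101, whose serum levels are expected to be below quantification, and it does not measure fetal risk.

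**The case against.** The strongest case is that the protocol already reaches these pregnancies by other routes. The opening duty in 7.2.2 has no day limit. Participation runs to the final contact, survival contacts are planned every three months for up to 2 years after the last dose, and the trial ends at the last study call or visit. On that reading, a pregnancy volunteered on day 60 is reportable. This stands as a possible reading. It also means that 7.2.2 gives two different end points in consecutive paragraphs, and a site may reasonably let the more specific one govern.

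Three stronger readings are tempting, and the documents do not support them.
- *Partner pregnancies after day 14 need not be reported.* Section 5.8.3 requires them to be reported and sets no day limit. Its limit to pregnancies on treatment applies to female subjects only. The weakness is the reference to 7.2.2, which does not speak of partners.
- *The protocol defines 120 days as the period of fetal or sperm effects.* It defines a contraception period and gives possible fetal harm as the reason. A contraception period and a reporting window of different lengths can both be obeyed, so this is a mismatch of purpose and not a strict contradiction.
- *The information is lost for good.* A related congenital anomaly is reportable at any time under 7.2.3.1. That backstop is partial: it needs a serious event, a judgment of relatedness and an investigator who hears of it. It captures neither the pregnancy nor a normal outcome, so it supplies no denominator.

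It is also fair to say that few pregnancies are likely among about 64 subjects with advanced malignancy under mandatory contraception.

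**Conclusion.** The point holds for female subjects: 88% of the post-dose contraception period lies outside the explicit reporting window. A reader might extend that percentage to the whole period at risk, but from first dose the share is 40% for a subject who completes 8 cycles and exceeds half only with shorter treatment. For partners of male subjects, the finding is an unclear duty, not a missing one. The conclusion assumes that a site would follow the 14-day sentence over the broader opening sentence, which is a reasonable but not the only reading. The persistence figures support the concern, but the conclusion does not depend on them. The change should be made because it is cheap and the data are scarce. It does not put the trial's primary objective at risk.

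**What to change.** Reconcile the two duties within 7.2.2 with each other and with 5.1.2, 5.8.2 and 5.8.3. State one pregnancy-reporting period that runs through the contraception period the protocol already sets, anchored to the last dose of either drug. Name both groups it applies to: female subjects and partners of male subjects. Then let 5.8.3 refer to that sentence. The contraception requirement itself is not in question here.

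The cost is a sentence or two of text and a few more reports to collect and follow to completion. No visit is added: subjects can be reminded at the 30-day safety visit, and the existing survival contacts can carry the question. One practical consequence should be planned for. Section 8.2 locks the database about 24 weeks (168 days) after the last subject enrolls, whereas 120 days after a Day 148 dose is Day 268. Late reports from the last subjects would therefore need to come in through safety reporting after lock.

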7.2.3 Immediate Reporting of Adverse Events to the Sponsor

7.2.3.1 Serious Adverse Events

A serious adverse event is any adverse event occurring at any dose or during any use of Sponsor's product that:

- Results in death;
- Is life threatening;
- Results in persistent or significant disability/incapacity;
- Results in or prolongs an existing inpatient hospitalization;
- Is a congenital anomaly/birth defect;
- Is an other important medical event.

Note: In addition to the above criteria, adverse events meeting either of the below criteria, although not serious per ICH definition, are reportable to the Sponsor in the same timeframe as SAEs to meet certain local requirements. Therefore, these events are considered serious by the Sponsor for collection purposes.

- Is a new cancer (that is not a condition of the study);
- Is associated with an overdose.

Refer to [Table 11](#) for additional details regarding each of the above criteria.

Progression of the cancer under study is not considered an adverse event unless it results in hospitalization or death.

For the time period beginning when the consent form is signed until treatment allocation/randomization, any serious adverse event, or follow up to a serious adverse event, including death due to any cause, that occurs to any subject must be reported within 24 hours to the Sponsor if it causes the subject to be excluded from the trial, or is the result of a protocol-specified intervention, including but not limited to washout or discontinuation of usual therapy, diet, placebo treatment or a procedure.

For the time period beginning at treatment allocation/randomization through 14 days following cessation of treatment, any serious adverse event, or follow up to a serious adverse event, including death due to any cause, whether or not related to the Sponsor's product, must be reported within 24 hours to the Sponsor either by electronic media or paper. Electronic reporting procedures can be found in the EDC data entry guidelines. Paper reporting procedures can be found in the Investigator Trial File Binder (or equivalent).

Additionally, any serious adverse event, considered by an investigator who is a qualified physician to be related to the Sponsor's product that is brought to the attention of the investigator at any time outside of the time period specified in the previous paragraph also must be reported immediately to the Sponsor.

All subjects with serious adverse events must be followed up for outcome.

7.2.3.2 Events of Clinical Interest

Selected non-serious and serious adverse events are also known as Events of Clinical Interest (ECI) and must be reported to the Sponsor.

For the time period beginning when the consent form is signed until treatment allocation/randomization, any ECI, or follow up to an ECI, that occurs to any subject must be reported within 24 hours to the Sponsor if it causes the subject to be excluded from the trial, or is the result of a protocol-specified intervention, including but not limited to washout or discontinuation of usual therapy, diet, placebo treatment or a procedure.

For the time period beginning at treatment allocation/randomization through 14 days following cessation of treatment, any ECI, or follow up to an ECI, whether or not related to the Sponsor's product, must be reported within 24 hours to the Sponsor, either by electronic media or paper. Electronic reporting procedures can be found in the EDC data entry guidelines. Paper reporting procedures can be found in the Investigator Trial File Binder (or equivalent).

Events of clinical interest for this trial include:

1. an overdose of Sponsor's product, as defined in Section 7.2.1 - Definition of an Overdose for This Protocol and Reporting of Overdose to the Sponsor, that is not associated with clinical symptoms or abnormal laboratory results.
2. an elevated AST or ALT lab value that is greater than or equal to 3X the upper limit of normal and an elevated total bilirubin lab value that is greater than or equal to 2X the upper limit of normal and, at the same time, an alkaline phosphatase lab value that is less

than 2X the upper limit of normal, as determined by way of protocol-specified laboratory testing or unscheduled laboratory testing.*

*Note: These criteria are based upon available regulatory guidance documents. The purpose of the criteria is to specify a threshold of abnormal hepatic tests that may require an additional evaluation for an underlying etiology. The trial site guidance for assessment and follow up of these criteria can be found in the Investigator Trial File Binder (or equivalent).

7.2.4 Evaluating Adverse Events

An investigator who is a qualified physician will evaluate all adverse events according to the NCI Common Terminology for Adverse Events (CTCAE), version 4.0. Any adverse event which changes CTCAE grade over the course of a given episode will have each change of grade recorded on the adverse event case report forms/worksheets.

All adverse events regardless of CTCAE grade must also be evaluated for seriousness.

For studies in which multiple agents are administered as part of a combination regimen, the investigator may attribute each adverse event causality to the combination regimen or to a single agent of the combination. In general, causality attribution should be assigned to the combination regimen (i.e., to all agents in the regimen). However, causality attribution may be assigned to a single agent if in the investigator's opinion, there is sufficient data to support full attribution of the adverse experience to the single agent.

Table 11 Evaluating Adverse Events

An investigator who is a qualified physician, will evaluate all adverse events as to:

V4.0 CTCAE Grading	Grade 1	Mild; asymptomatic or mild symptoms; clinical or diagnostic observations only; intervention not indicated.
	Grade 2	Moderate; minimal, local or noninvasive intervention indicated; limiting age-appropriate instrumental ADL.
	Grade 3	Severe or medically significant but not immediately life-threatening; hospitalization or prolongation or hospitalization indicated; disabling; limiting self-care ADL.
	Grade 4	Life threatening consequences; urgent intervention indicated.
	Grade 5	Death related to AE
Seriousness	A serious adverse event is any adverse event occurring at any dose or during any use of Sponsor's product that:	
	† Results in death ; or	
	† Is life threatening ; or places the subject, in the view of the investigator, at immediate risk of death from the event as it occurred (Note: This does not include an adverse event that, had it occurred in a more severe form, might have caused death.); or	
	† Results in a persistent or significant disability/incapacity (substantial disruption of one's ability to conduct normal life functions); or	
	† Results in or prolongs an existing inpatient hospitalization (hospitalization is defined as an inpatient admission, regardless of length of stay, even if the hospitalization is a precautionary measure for continued observation. (Note: Hospitalization for an elective procedure to treat a pre-existing condition that has not worsened is not a serious adverse event. A pre-existing condition is a clinical condition that is diagnosed prior to the use of a Merck product and is documented in the patient's medical history.); or	
	† Is a congenital anomaly/birth defect (in offspring of subject taking the product regardless of time to diagnosis); or	
	Is a new cancer (that is not a condition of the study) (although not serious per ICH definition, is reportable to the Sponsor within 24 hours to meet certain local requirements); or	
	Is an overdose (whether accidental or intentional). Any adverse event associated with an overdose is considered a serious adverse event for collection purposes. An overdose that is not associated with an adverse event is considered a non-serious event of clinical interest and must be reported within 24 hours.	
	Other important medical events that may not result in death, not be life threatening, or not require hospitalization may be considered a serious adverse event when, based upon appropriate medical judgment, the event may jeopardize the subject and may require medical or surgical intervention to prevent one of the outcomes listed previously (designated above by a †).	
Duration	Record the start and stop dates of the adverse event. If less than 1 day, indicate the appropriate length of time and units	
Action taken	Did the adverse event cause the Sponsor's product to be discontinued?	
Relationship to Sponsor's Product	Did the Sponsor's product cause the adverse event? The determination of the likelihood that the Sponsor's product caused the adverse event will be provided by an investigator who is a qualified physician. The investigator's signed/dated initials on the source document or worksheet that supports the causality noted on the AE form, ensures that a medically qualified assessment of causality was done. This initialed document must be retained for the required regulatory time frame. The criteria below are intended as reference guidelines to assist the investigator in assessing the likelihood of a relationship between the test drug and the adverse event based upon the available information. The following components are to be used to assess the relationship between the Sponsor's product and the AE ; the greater the correlation with the components and their respective elements (in number and/or intensity), the more likely the Sponsor's product caused the adverse event (AE):	
	Exposure	Is there evidence that the subject was actually exposed to the Sponsor's product such as: reliable history, acceptable compliance assessment (pill count, diary, etc.), expected pharmacologic effect, or measurement of drug/metabolite in bodily specimen?
	Time Course	Did the AE follow in a reasonable temporal sequence from administration of the Sponsor's product? Is the time of onset of the AE compatible with a drug-induced effect (applies to trials with investigational medicinal product)?
	Likely Cause	Is the AE not reasonably explained by another etiology such as underlying disease, other drug(s)/vaccine(s), or other host or environmental factors

Relationship to Sponsor's Product (continued)	The following components are to be used to assess the relationship between the test drug and the AE: (continued)	
	Dechallenge	Was the Sponsor's product discontinued or dose/exposure/frequency reduced? If yes, did the AE resolve or improve? If yes, this is a positive dechallenge. If no, this is a negative dechallenge. (Note: This criterion is not applicable if: (1) the AE resulted in death or permanent disability; (2) the AE resolved/improved despite continuation of the Sponsor's product; or (3) the trial is a single-dose drug trial); or (4) Sponsor's product(s) is/are only used one time.)
	Rechallenge	Was the subject re-exposed to the Sponsor's product in this study? If yes, did the AE recur or worsen? If yes, this is a positive rechallenge. If no, this is a negative rechallenge. (Note: This criterion is not applicable if: (1) the initial AE resulted in death or permanent disability, or (2) the trial is a single-dose drug trial); or (3) Sponsor's product(s) is/are used only one time). NOTE: IF A RECHALLENGE IS PLANNED FOR AN ADVERSE EVENT WHICH WAS SERIOUS AND WHICH MAY HAVE BEEN CAUSED BY THE SPONSOR'S PRODUCT, OR IF REEXPOSURE TO THE SPONSOR'S PRODUCT POSES ADDITIONAL POTENTIAL SIGNIFICANT RISK TO THE SUBJECT, THEN THE RECHALLENGE MUST BE APPROVED IN ADVANCE BY THE SPONSOR CLINICAL DIRECTOR AS PER DOSE MODIFICATION GUIDELINES IN THE PROTOCOL.
		The assessment of relationship will be reported on the case report forms /worksheets by an investigator who is a qualified physician according to his/her best clinical judgment, including consideration of the above elements.
Record one of the following		Use the following scale of criteria as guidance (not all criteria must be present to be indicative of a Sponsor's product relationship).
Yes, there is a reasonable possibility of Sponsor's product relationship.	There is evidence of exposure to the Sponsor's product. The temporal sequence of the AE onset relative to the administration of the Sponsor's product is reasonable. The AE is more likely explained by the Sponsor's product than by another cause.	
No, there is not a reasonable possibility of Sponsor's product relationship	Subject did not receive the Sponsor's product OR temporal sequence of the AE onset relative to administration of the Sponsor's product is not reasonable OR the AE is more likely explained by another cause than the Sponsor's product. (Also entered for a subject with overdose without an associated AE.)	

